The parallel study design allows for the examination of between-individual comparisons of test effects and within-individual longitudinal test effects (i.e. repeated daily CGM metrics). Significance level will be set at $\alpha = 0.05$. Covariates will include: age, sex, race/ethnicity, baseline cognitive ability (for cognitive outcomes only), baseline homeostatic model of insulin resistance (HOMA-IR), body fat mass (except for subgroup analysis by weight status), and Tanner stage. We will also evaluate for a weight status interaction (intervention x healthy weight / overweight).

The following analyses will be performed:

- i.** Participant characteristics will be summarized using means (standard deviations) and frequencies.
- ii.** Baseline (time 0) values for participant characteristics, insulin, glucose, heart rate, and blood pressure between the groups will be compared using t-tests.
- iii.** The primary analysis will be ANCOVA comparing children randomized to the two groups for insulin iAUC at the end-study oral glucose tolerance test, with age, sex, race/ethnicity, HOMA-IR, body fat mass, and Tanner stage as variables in the model. If all covariates are nonsignificant, unpaired t-tests will be reported for the differences in OGTT insulin iAUC by condition (prolonged vs interrupted sitting). Similar analyses will be used to examine glucose iAUC, 5- or 6-day average 24hr CGM iAUC and 24hr MAGE. (Subjects may only have 5 days of CGM data if a device is

accidentally removed and replaced at the next visit or subject uses a medication that interacts with glucose readings such as acetaminophen-after which 24hrs of data will be omitted from analysis). Mixed models will also be used to assess the influence of prolonged vs. interrupted sitting on insulin and glucose iAUC over the 3 hours of observation. To evaluate differences in the dependent variables at each time point, planned comparisons of model-based mean differences between each time points will be calculated. Additionally, mixed models will be used to assess condition influence on mean 24hr CGM glucose iAUC and 24hr MAGE.

- iv. ANCOVA or (as indicated above) t-tests will investigate differences in working memory, inhibition, attention, processing speed, mood, anxiety, and kcal intake between prolonged sitting and interrupted sitting at the post- test.

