- v. Mixed models will also be used to assess the influence of prolonged vs. interrupted sitting on change in cognitive function, mood and anxiety (pre-post test scores) controlled for significant covariates. Covariates to be considered include those listed above in addition to free living activity and sleep.
- vi. As a secondary analysis, all the analyses described above will be performed on the subgroups: Healthy weight and overweight subjects.
- vii. Supplemental MRS Study: Repeated measures ANOVA will investigate the change in IMCL content between baseline & pre-session (thus, evaluating for daily intervention effect) as well as immediately pre- and post-intervention session (thus, evaluating the immediate effect of intervention) by condition. ANCOVA analyses will compare the change in IMCL content by condition with age, sex, race/ethnicity, HOMA-IR, body fat mass, and Tanner stage as variables in the model.

b. Power Analysis

Based on our preliminary published data,⁶⁵ and our unpublished data in overweight youth, we expect a moderate to large (Cohen's $d = 0.8$) effect size. With an 80% power, $\alpha=0.05$, our sample size requires evaluable data from 21 in each group; with our goal of subgroup analysis within healthy weight and overweight groups, we will require 84 participants total (42 overweight and 42 healthy weight). This is supported by previously reported adult data published by Dunstan et al. who identified the mean (standard

deviation) difference between the two groups was 191.0 (334.9) pmol/L yielding a moderate to large effect size.⁴⁸ Taking into consideration more variability due to the parallel design (versus cross over designs used previously), we will randomize up to 120 participants and estimate that at most 36 children will drop-out of the study before completion. We expect at least 84 participants to complete the protocol which is our target completion based on these analyses.

11. Human Participant Protections

a. Rationale for subject selection

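### The 21 per group in Section 10.b matches a one-sided test that the plan never declares; two-sided and unadjusted, each weight-group analysis has about 72% power at 84 completers, not 80%

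*Combined protocol and SAP*

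**What the plan says.** Section 10.b gives all the planning inputs: Cohen's d = 0.8, 80% power and alpha 0.05. From these it states that "our sample size requires evaluable data from 21 in each group". The total follows from the weight-group aim: "with our goal of subgroup analysis within healthy weight and overweight groups, we will require 84 participants total (42 overweight and 42 healthy weight". The same section confirms the target: "We expect at least 84 participants to complete the protocol which is our target completion based on these analyses". Up to 120 children are randomized and at most 36 losses are expected; Section 3.a repeats these figures.

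On the analyses, Section 10.a says "Significance level will be set at" 0.05 and does not mention the number of sides. Item iii states "The primary analysis will be ANCOVA comparing children randomized to the two groups for insulin iAUC at the end-study oral glucose tolerance test", with covariates, and an unpaired t-test is reported if none of the covariates is significant. Item vi adds: "As a secondary analysis, all the analyses described above will be performed on the subgroups: Healthy weight and overweight subjects". Hypotheses 1a and 1b in Section 2 are directional (lower insulin and glucose measures with interruption), while Hypothesis 2 expects no difference.

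Two supporting remarks appear in 10.b. An adult study is cited, in which the "difference between the two groups was 191.0 (334.9) pmol/L yielding a moderate to large effect size". The enrolment figure is explained as follows: "Taking into consideration more variability due to the parallel design (versus cross over designs used previously), we will randomize up to 120 participants".

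**The concern.** The weight-group aim is the only reason given for 84 completers instead of 42, so the stated 80% power belongs to the weight-group analyses. With d = 0.8, 21 per arm is too few for 80% power in a two-sided t-test at 0.05. If testing is two-sided, as readers will normally assume, the plan overstates the power of the analyses that set its sample size.

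What is at stake is how a null result in one weight group would be read. Section 9.b intends these analyses to show whether the intervention works differently by weight status. A reader who trusts the 80% would expect a true d = 0.8 to be missed 20% of the time. Two-sided and unadjusted, at the planned minimum, it would be missed about 28% of the time.

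**Working it through.** **Inputs.** From 10.b: d = 0.8, alpha = 0.05, power 80%, 21 per arm within a weight group, 84 completers, 120 randomized, at most 36 losses. Equal arms are implied by 21 in each group.

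**Formula.** For two equal arms of n, the t statistic has df = 2n − 2 and noncentrality d × √(n/2). Power is the probability that it exceeds the critical t (in either direction if two-sided).

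**Reproducing the 21.** One-sided at 0.05, the required n is 20.03, which rounds up to 21.
- n = 20: noncentrality 2.530, critical t 1.686, power 79.9%.
- n = 21: noncentrality 0.8 × √10.5 = 2.592, critical t 1.684, power 81.7%.

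**Two-sided, same inputs.** The required n is 25.52, which rounds up to 26.
- n = 21: noncentrality 2.592, critical t 2.021, power 71.6%.
- n = 25: 79.1%.
- n = 26: 80.7%.

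So 80% power needs 26 × 2 arms × 2 weight groups = 104 completers. At 21 per arm, the effect detectable with 80% power is d = 0.89.

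**Effect of losses.** Assuming losses fall evenly over arms and weight groups, n per arm per weight group = (120 − losses)/4. Two-sided, unadjusted, d = 0.8:

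| Losses of 120 | n per arm | Power |
|---|---|---|
| 0 | 30 | 86.1% |
| 12 | 27 | 82.2% |
| 16 | 26 | 80.7% |
| 24 | 24 | 77.4% |
| 36 | 21 | 71.6% |

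The 80% therefore holds up to about 16 losses (16/120 = 13%), against a planned maximum of 36 (36/120 = 30%).

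**Effect of covariates.** If covariates explain a share R² of the outcome variance, the noncentrality becomes d × √(n/2)/√(1 − R²). With an assumed 7 covariate degrees of freedom, df = 40 − 7 = 33. At 21 per arm, two-sided:
- R² = 0.1: 75.6%
- R² = 0.2: 80.3%
- R² = 0.3: 85.2%

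The plan gives no R², so this range is an assumption.

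**Pooled primary comparison.** Two-sided, unadjusted, 42 against 42: 95.2% at d = 0.8, and 80% for d = 0.62.

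**The two supporting remarks.** At face value the adult ratio is 191.0/334.9 = 0.57, from a crossover study. That roughly fits the description moderate to large, but it is below the 0.8 used. On enrolment, 120 − 36 = 84, so at the assumed maximum loss nothing remains as an allowance for parallel-design variability. With fewer losses the surplus over 84 does add precision.

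**The case against.** The strongest reply is that 21 need not come from a one-sided test. The planned model is ANCOVA, and with R² of about 0.2 a two-sided ANCOVA also reaches 80% at 21 per arm. Baseline HOMA-IR is a covariate for an insulin outcome, so some gain is plausible, and the unadjusted t-test is only the fallback when no covariate is significant. It can also be said that directional hypotheses make a one-sided test natural, that no passage declares two-sided testing either, that the weight-group analyses are secondary in a study described as a pilot, that 72% applies only at the largest planned loss, and that the weight-status interaction in 10.a is the direct test of differential effect.

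Much of this stands, and it limits the point. The covariate explanation cannot be excluded. However, 10.b mentions no adjustment and no R², and 10.a drops body fat mass from the weight-group models. A directional hypothesis does not by itself declare a one-sided test, and the single alpha statement also covers Hypothesis 2, which is not directional. The interaction test does not change the power stated for each weight group. Whichever explanation is true, the assumption that yields 80% is missing from the plan.

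The adult ratio and the parallel-design allowance are side notes. The published source is not available here, a crossover ratio may not be comparable with a parallel-group d, and the main point does not depend on either note.

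**Conclusion.** The concern holds. The stated 80% at 21 per arm is right for a one-sided t-test, which the plan does not declare. Two-sided and unadjusted, each weight-group analysis has about 72% power at 84 completers if d = 0.8 and the arms split 21 and 21; 80% needs 104 completers. The shortfall disappears with about 16 or fewer evenly spread losses, or with covariates explaining about 20% of the variance. The pooled primary analysis is not affected. The choice of 0.8 as planning value is not disputed. This should be fixed, because the stated power is not delivered on the ordinary two-sided reading and the correction is simple.

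**What to change.** Revise the wording of Section 10.b:
- State whether tests are one-sided or two-sided. If one-sided testing was intended, declare it and name the hypotheses it covers.
- If two-sided, restate the unadjusted power at 84 completers: about 72% per weight group at d = 0.8 (80% for d = 0.89), and about 95% pooled at d = 0.8 (80% for d = 0.62). The sponsor may add that weight-group power is about 81% at 104 completers and 86% at 120.
- If the covariates are relied on, state the assumed R²; about 0.2 gives 80%.
- Optionally, note that the adult ratio is 0.57 at face value and comes from a crossover, and that the 120 adds precision only when fewer than 36 children are lost.

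The cost is a less favourable stated power for the weight-group analyses. No extra children are needed, and procedures and analyses stay as they are.
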